6.11.3.3 Time to Progression and Progression Free Survival

TTP and PFS will be analyzed and presented separately for each age cohort, and censoring rules will be applied as laid out in Section 4.1.3.6 and Section 4.1.3.7 respectively.

TTP and PFS will each be analyzed using KM methods; with median, lower, and upper quartile estimate and associated 95% Cls (using the Brookmeyer-Crowley method), the number of participants with events or who are censored, as well as reason for censoring, will be presented separately by age cohort. "NE" will be presented where estimates of such were not estimable. Additionally, KM plots will be presented by age cohort. These presentations will be produced for the FAS as a whole and for the subgroup of participants in the FAS who have an investigator determination of progressive disease at baseline.

The sensitivity analyses of TTP and PFS using REiNS criteria as outlined in Section 4.1.3.6.1 and Section 4.1.3.7.1 will also be summarized using the same method as described above.

Document: S:\Q_146\Q_03974\MEK-NF-201\Prog_Stat\Documentation\SAP\MEK-NF-201 SAP v1.0.0.docx

Author:

6.11.3.4 Patient Global Impression of Change/Severity

All PGIS and PGIC data will be listed by participant and visit.

The absolute count and percentage of participants in each of the PGIS and PGIC categories, as defined in Appendix 1.1 and Appendix 1.2 respectively, will be summarized separately by visit and by confirmed objective response status.

6.11.3.5 Acceptability of Tablet Formation (Pediatric Oral Medicines Acceptability Questionnaire)

All P-OMAQ-P and P-OMAQ-C data will be listed by participant.

P-OMAQ-P and P-OMAQ-C individual question scores and total scores will be summarized separately, the summaries presented will be the mean, SD, median, minimum, and maximum values. For these summaries data from all visits in either phase will be pooled.

6.11.3.6 Change in Tumor Volume

Target tumor volume, change from baseline in tumor volume, and percentage change from baseline in tumor volume calculated as per Section 5.1.2 will be summarized by the number of participants, mean, SD, median, minimum, and maximum values by visit for each age cohort separately. This will be presented by averaging the volume across the two readers (unless response adjudication was performed) and reported separately for each reader (A vs B) from the BICR data, since the volumetric measurement was not triggered for adjudication.

An MMRM will be fit separately by age cohort with change from baseline in tumor volume as the dependent variable, visit as a fixed effect and baseline tumor volume as a covariate. The covariance structure will be decided in the manner described in Section 6.11.2.2, and a Kenward-Roger approximation will be used for the degrees of freedom. This model will be fitted for each cohort for all scheduled visits up until the first point where there are fewer than 5 participants with valid tumor volume measurements. EOT visits will be mapped to the closest scheduled tumor visit following the rules outlined in Table 12 and will only be included in the model if the participant has no other record at that timepoint. LS Means estimates will be presented with associated standard errors, 95% Cls and p-values by visit. Plots of the LS Means estimates over time with associated 95% Cl bands will be presented separately by age cohort.

Best volumetric percentage change from baseline as well as the time, in months, to the best volumetric percentage change from baseline will be summarized by the number of participants, mean, SD, median, minimum, and maximum. This will be presented by averaging the volume across the two readers (unless response adjudication was performed) and reported separately for each reader (A vs B) from the BICR data. In addition, a waterfall plot of the best volumetric % change from baseline will be presented using the average (unless adjudication of response occurred), and by the two readers separately.

6.11.3.7 Disease Control Rate

The number and percentage of participants achieving disease control and accompanying DCR by the end of the treatment phase will be presented by age cohort, alongside the corresponding 2-sided Clopper-Pearson 95% Cl.

Document: S:\Q_146\Q_03974\MEK-NF-201\Prog_Stat\Documentation\SAP\MEK-NF-201 SAP v1.0.0.docx

Author:

6.11.3.8 Time to Response

Time to response will also be summarized for confirmed responders by age cohort and is defined as the time in months from the start of treatment to the date of first response that was subsequently confirmed. Summary statistics presented will include mean, SD, median, minimum, and maximum. The time to response will be summarized for the primary endpoint and by each of the two readers separately for the FAS.

6.12 Other Analyses

6.12.1 Safety Analyses

All safety analyses will be performed on the Safety Analysis Set as defined in Section 3.3.

6.12.1.1 Adverse Events

Only TEAEs will be presented in summary tables, as defined in Section 4.2.2.1. An overview of these TEAEs will be presented by age cohort summarizing the number and percentages of participants with TEAEs; SAEs; TEAEs of at least Grade 3 severity; study-drug related AEs; and AEs leading to dose modification, interruption, reduction, and discontinuation. The number and percentage of participants with a maximum recorded toxicity Grade 1-5 will also be presented.

Separate summaries by SOC and PT will be provided for the incidence of TEAEs (also for TEAEs by PT only), incidence of TEAEs by highest severity, incidence of SAEs, TEAEs of at least Grade 3 severity, study drug-related TEAEs, study drug related SAEs, study drug-related TEAEs of at least Grade 3 severity, study procedure related TEAEs, TEAEs leading to discontinuation, most common TEAEs related to study drug (occurring in ≥5% of overall cohort), TEAEs leading to dose reduction, TEAEs leading to dose interruption and AESIs – all as defined in Section 4.2.2.1. In addition, a summary of TEAEs by PT only will also be presented. All summaries will present absolute participant counts (n) and TEAE event counts. Percentages (%) will be calculated based on the number of participants at risk. Additionally, TEAEs will be summarized by cycle of first onset (After Cycle 6, cycles will be grouped either as Cycles 7-12, or Cycle 13 and later).

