- 13. Tumor (core needle) biopsy (Section 8.1.6) This assessment may occur during the Screening period, but must be performed after the Screening MRI volumetric assessment has been confirmed evaluable by central radiologic review and prior to first dose of study treatment. Tumor biopsy will be utilized for PD tumor response in participants ≥ 18 years of age. Participants 2 to 17 years of age should not undergo biopsy unless there is a clinical indication to obtain fresh tumor tissue. If a study biopsy was collected and the participant did not initiate study treatment, this biopsy may be utilized as the baseline biopsy if the participant subsequently re-screens for enrollment.
- 14. Ophthalmic assessments (Section 8.2.7) will include slit lamp with binocular indirect ophthalmoscopy and intraocular pressure measurements. Assessments must be performed by an ophthalmologist. Participants in the pediatric cohort must be evaluated by a pediatric ophthalmologist.
- 15. 12-Lead Electrocardiograms (ECGs) (Section 8.2.4) should be administered in triplicate (approximately 2-3 minutes apart and averaged) and read locally at the Site. Participants should rest in semi-recumbent supine position for at least 5 minutes prior to ECG collection.
 - 15a. At Cycle 1 Day 1, triplicate ECGs are required prior to the first dose of study treatment and approximately 1-hour post dose.
 - **15b.** At Cycle 1 Day 15, triplicate ECGs are required 1-hour post dose of study treatment with a ±10-minute allowed window.
 - 15c. Triplicate ECG may be conducted at any time during the visit after completion of applicable PROs.
- 16. Echocardiogram (Section 8.2.8): Left ventricular ejection fraction (LVEF) will be assessed via echocardiogram.
 - 16a. Echocardiogram required at Screening to confirm or re-confirm Exclusion Criterion 11 and will serve as the Baseline echocardiogram throughout the study.
 - **16b.** Echocardiogram at the ET visit only required if not performed within the past 1 month.
- 17. Strength assessment (Section 8.1.3) will be measured utilizing a dynamometer and Medical Research Council (MRC) Muscle Scale for participants with a target plexiform neurofibroma (PN) that causes motor dysfunction or weakness. The MRC grading assessment should be conducted prior to the dynamometer assessment. Must be done prior to first dose of study treatment at the Baseline visit. Strength assessment at the early termination (ET) visit only required if not performed within the past 1 month.

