8.1.6. Target Tumor Biopsy

For participants ≥ 18 years of age, a core needle or Tru-Cut needle biopsy of the target tumor will be performed at Baseline in the Treatment Phase prior to receiving any study treatment and after the MRI volumetric assessment has been confirmed evaluable by central radiologic review. This is a percutaneous biopsy method using a hollow-bored needle to obtain a volume of tissue in order to assess both cellular and architectural information. A 16-gauge needle or larger must be used. Fine needle aspirates are not acceptable. Participants 2 to 17 years of age should not undergo biopsy unless there is a clinical indication to obtain fresh tumor tissue. If a pediatric participant turns 18 years old during study participation, a biopsy is not required at the Cycle 24/Early Termination visit of the Treatment Phase. If a study biopsy was collected and the participant did not initiate study treatment, this biopsy may be utilized as the baseline biopsy if the participant subsequently re-screens for enrollment. If the participant did not have evaluable biopsy tissue at Baseline, they are not required to provide an End of Treatment biopsy of the target tumor.

Refer to Section 10.8 for the sampling schedule and the central laboratory manual for instructions for handling, processing and shipment of tumor biopsies.

8.1.7. 6-Minute Walk Test

Participants with a target PN that causes airway or lower extremity motor dysfunction will undergo a 6-Minute Walk Test in accordance with the SoA (Section 1.3) during the Treatment Phase. This assessment must always be completed after the Strength (Section 8.1.3) and Range

of Motion (Section 8.1.5) assessments. This evaluation should be performed by Rehabilitation Medicine, Physiatry, or Physical Therapy, if possible, and should ideally be completed by the same examiner at each visit, if feasible. Refer to the study reference manual for additional instructions.

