8.3.2. Time Period and Frequency for Collecting AE and SAE Information

All SAEs and AEs will be collected from the time of signing informed consent/assent until 30 days after the last dose of study treatment at the time points specified in the SoA (Section 1.3, Section 1.4).

Medical occurrences that begin before the start of study treatment but after obtaining informed consent/assent will be recorded as AEs.

All SAEs will be recorded and reported to the Sponsor's safety group (Safety) immediately and under no circumstance should this exceed 24 hours, as indicated in Section 10.3.3 and Section 10.3.4. The Investigator will submit any updated SAE data to Safety within 24 hours of it being available.

To report the SAE, a paper SAE form must be completed, scanned, and emailed Safety at [contact]. The paper SAE form can be found in the Site reference manual. Refer to Section 10.3.4 for more details on reporting SAEs to Safety.

Investigators are not obligated to actively seek AEs and/or SAEs after conclusion of the study participation. However, if the Investigator learns of any SAE, including a death, at any time after a participant has been discharged from the study and considers the event to be reasonably related to the study treatment or study participation, the Investigator must promptly notify the Sponsor.

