9.4.2. Safety Analyses

All safety analyses will be performed on the Safety Population.

Endpoint	Statistical Analysis Methods
Safety Endpoints	The safety and tolerability of mirdametinib (PD-0325901) will be evaluated by means of study drug-related adverse event reports, physical examinations, and laboratory safety evaluations. National Cancer Institute CTCAE Version 5.0 will be used for grading of adverse events. Investigators will provide their assessment as related to treatment (definite, probable, or possible relationship).
	The incidence of treatment-emergent adverse events, SAEs, adverse events of at least Grade 3 in severity, study drug-related adverse events, and adverse events leading to withdrawal of study drug will be summarized. Treatment-emergent adverse events will be those that start or worsen on or after the first day of study drug through 30 days after the last dose of study drug; related adverse events will be those with an Investigator determination of related to treatment.
	Laboratory data will be analyzed by summary statistics over time, as well as by shift tables based on NCI CTCAE Version 5.0 grades of severity. In addition, ECG intervals will be summarized by visit. The number and percentage of participants who have a post-Baseline QTcF between 450 and 480, > 480, and > 500, as well as the number and percentage of participants who have a change from Baseline in QTcF of < 30, 30 to 60, and > 60 will be summarized.

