4.2.1.1 Adverse Event Definitions

Certain AEs are specified as adverse events of special interest (AESI). AESIs for this study were marked by the investigators and will be reported as such. AESIs include but are not limited to the following cases in Table 8.

Table 8: Adverse Events of Special Interest

Gastrointestinal (reported as AESI if Grade ≥3)		
Diarrhea	Nausea	Vomiting
Eye Disorders (reported as A		
Retinal Vein Occlusion (RVO)		Optic neuropathy
Retinopathy	Retinal detachment	
Cardiac Disorders (reported as AESI if Grade ≥2)		
Ejection fraction decreased		Left ventricular dysfunction
Neurological Disorders (reported as AESI if Grade ≥2)		
Confusion	Hallucinations	Delirium
Infections and Infestations (r	eported as AESI if Grade ≥3)	
Viral Rash		
Skin Disorders (reported as AESI if Grade ≥3)		
Rash*	Acneiform Rash*	

^{*}Rash and Acneiform Rash were considered an AESI for Grade ≥2 in earlier versions of the protocol. Due to this, there may be some Grade 2 rashes marked as AESIs by the investigators, which will be reported as such.

The AESI of "Rash" is a composite term, all PTs which will be considered as a "Rash" AESI are listed in Appendix 2.

AEs will be summarized combined across the Treatment and LTFU phases. A TEAE is defined as an AE that starts or worsens on or after the first dose of study treatment is taken, including those occurring or increasing in severity up to 30 days after the last dose of study treatment.

A treatment-emergent serious adverse event (SAE) is defined as a TEAE that, at any dose; results in death; is life-threatening; requires inpatient hospitalization or prolongation of existing hospitalization; results in persistent disability/incapacity; is a congenital anomaly/birth defect; or is assessed by the investigator as an otherwise important serious medical event.

Document: S:\Q_146\Q_03974\MEK-NF-201\Prog_Stat\Documentation\SAP\MEK-NF-201	SAP
v1.0.0.docx	
Author	

An AE will be classified as a study treatment-related AE if it has an investigator determination of related to study treatment. Investigators will provide their assessment as related to study treatment, not related to study treatment, or not applicable. AEs that are missing a treatment related/unrelated classification will not be imputed and "missing" will be presented as a category in summary tables.

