An AE will be classified as a study procedure-related adverse event if it has an investigator determination of related to study procedure. Investigators will provide their assessment as related to study procedure, not related to study procedure, or not applicable. AEs that are missing a study procedure related/unrelated classification will not be imputed and "missing" will be presented as a category in summary tables.

Additionally, the following terms are defined:

- Adverse reaction (AR) any noxious and unintended response to a medical product or procedure, for which a causal relationship with the product or procedure is at least a reasonable possibility (i.e., the relationship cannot be ruled out).
- Serious adverse reaction (SAR) an SAE for which a causal relationship with the product or procedure is at least a reasonable possibility (i.e., the relationship cannot be ruled out).
- Suspected unexpected serious adverse reaction (SUSAR) an SAR that is judged as unexpected. An event is considered "unexpected" if it is not listed as expected in the reference safety information (RSI) section of the investigator brochure (IB) or summary of product characteristics.

The intensity of all AEs will be graded according to the NCI Common Terminology Criteria for Adverse Events (CTCAE) Version 5.0. For AEs not listed in the CTCAE, the following grading system should be used:

- CTCAE Grade 1 Mild; asymptomatic or mild symptoms; clinical or diagnostic observations only; treatment not indicated.
- CTCAE Grade 2 Moderate; minimal, local, or noninvasive treatment indicated; limiting age-appropriate instrumental activities of daily living (ADL)*.
- CTCAE Grade 3 Severe or medically significant but not immediately life-threatening; hospitalization or prolongation of hospitalization indicated; disabling; limiting self-care ADL**.
- CTCAE Grade 4 Life-threatening consequences; urgent treatment indicated.
- CTCAE Grade 5 Death related to AE.

*Instrumental ADL refer to preparing meals, shopping for groceries or clothes, using the telephone, managing money, etc.

**Self-care ADL refer to bathing, dressing and undressing, feeding self, using the toilet, taking medications, and not bedridden

An AE leading to study discontinuation will be defined as an AE where the primary reason for discontinuation of study (on the 'End of Study' CRF page) was recorded as being an AE.

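### The SAP's procedure-related adverse event table counts only treatment-emergent events, so complications of the adult baseline biopsy that start before the first dose and do not later worsen are left out

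*SAP*

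**What the plan says.** **The biopsy.** Protocol inclusion criterion 6 makes pre-treatment and end-of-treatment biopsies a condition of entry for adults. Protocol 8.1.6 fixes the timing of the first: a "biopsy of the target tumor will be performed at Baseline in the Treatment Phase prior to receiving any study treatment". Footnote 13 to the Treatment Phase schedule (Protocol 1.3) allows it during Screening, once central review has confirmed that the MRI is evaluable. Protocol Appendix 8 lists it as a Cycle 1 Day 1 pre-dose item.

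**Collection.** Protocol 8.3.2 collects AEs and SAEs from consent and says: "Medical occurrences that begin before the start of study treatment but after obtaining informed consent/assent will be recorded as AEs".

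**Definition.** SAP 4.2.1.1 defines procedure-relatedness by attribution, with no reference to dosing: "An AE will be classified as a study procedure-related adverse event if it has an investigator determination of related to study procedure".

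**Reporting.** SAP 6.12.1.1 says "Only TEAEs will be presented in summary tables", and its list of tables by system organ class and preferred term includes "study procedure related TEAEs, TEAEs leading to discontinuation". Under SAP 4.2.1.1, "A TEAE is defined as an AE that starts or worsens on or after the first dose of study treatment is taken", with the window closing 30 days after the last dose. SAP 6.12.1 runs all safety analyses on the Safety Analysis Set, which SAP 3.3 limits to participants who took at least one dose. No summary of pre-treatment AEs is planned. Section 6.12.1.1 does not mention an AE listing, although the SAP promises listings for disposition, demographics, medical history, concomitant medication and MRI data.

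**The concern.** Limiting drug-safety tables to treatment-emergent events is standard because exposure to the drug begins at the first dose. For a study procedure, exposure begins at the procedure. The SAP applies the drug clock to a table about procedures, and the main invasive procedure, the adult baseline biopsy, always happens before that clock starts.

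The biopsies serve pharmacodynamic biomarker work, an exploratory objective, so participants bear their risk for research purposes. The protocol itself describes these tumors as highly vascular (Introduction) and names vascularity and closeness to vital structures among the reasons for inoperability (inclusion criterion 4). A low count in the procedure-related table could be read as evidence that the biopsies were well tolerated, when part of the relevant period was never tabulated.

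**Working it through.** **1. Which biopsy events reach the table.** Applying SAP 4.2.1.1, 5.5.2.1 and 6.12.1.1 as written:

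| Event attributed to a study biopsy | In the table? |
|---|---|
| Baseline biopsy; complete onset date before first dose; no later worsening | No |
| Baseline biopsy; onset before first dose; worsens on or after first dose | Yes |
| Baseline biopsy; onset after first dose | Yes |
| Baseline biopsy; partial or missing onset date | Depends on imputation (step 2) |
| Cycle 24 or early-termination biopsy; onset within 30 days of last dose | Yes |
| Any biopsy in a person never dosed | No (outside the Safety Analysis Set) |

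The first row is the gap. It applies to serious events too, because SAP 4.2.1.1 defines its SAE category as a subset of treatment-emergent events and 6.12.1.1 confines every AE summary table to those events.

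**2. Imputation.** When the earliest possible start precedes treatment, SAP 5.5.2.1 imputes the minimum of the first-dose date, the latest possible start and the latest possible stop. An event with only month and year known, in the month of first dose, is moved to the first-dose date unless its latest possible stop is earlier. An event in an earlier month, or known to have stopped before dosing, stays pre-dose. So imputation brings in some first-row events but not all.

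**3. Day 1.** Protocol 9.4.2 uses a different boundary: "Treatment-emergent adverse events will be those that start or worsen on or after the first day of study drug". An onset on Day 1 after the biopsy but before the first dose counts under the protocol's day-level wording and not under the SAP's dose-level wording.

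**4. Size.** The plan gives no figure for this quantity. Its only safety figure is a 95% chance of seeing at least one event with a 3.0% rate in 100 participants. That reproduces: 1 − (1 − 0.03)^100 = 0.952.

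The same formula serves for illustration. Let n = 50 be the planned adult cohort with one baseline biopsy each, and let q be the chance that a biopsied adult has a complication in the first row of the table. Then q = c × s, where c is the complication rate per biopsy and s is the share of complications that start before dosing, do not worsen and are not moved by imputation. The documents give neither c nor s. Expected omissions are n × q, and the chance of at least one is 1 − (1 − q)^50, taking participants as independent.

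| Assumed q | Example of c × s | Expected omitted (50q) | Chance of at least one |
|---|---|---|---|
| 1% | 10% × 10% | 0.5 | 39% |
| 3% | 6% × 50% | 1.5 | 78% |
| 5% | 10% × 50% | 2.5 | 92% |
| 10% | 10% × 100% | 5.0 | 99% |

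The value n = 50 is the full-cohort case. Appendix 8, footnote c, allows for a participant without a pre-dose biopsy, so the actual number may be smaller.

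**The case against.** The safety objective concerns the drug, not the procedures. Protocol 9.4.2 asks for treatment-emergent summaries and no procedure-related analysis. The SAP's table is an addition, openly labelled as treatment-emergent. SAEs from consent reach the sponsor within 24 hours (Protocol 8.3.2), and the DMC reviews serious AE data (Protocol 9.5). Eligibility also screens out adults with a contraindication to serial biopsy. All of this is correct, and it means that the gap is one of reporting, not of collection or participant protection. It does not justify the table's scope: once the SAP defines procedure-related events and tabulates them, the window should match the procedure.

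Three stronger readings are tempting and are not supported.

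- *Baseline biopsy complications can never be tabulated, so the table may read zero.* Events that worsen after dosing count, later-onset events count, some partial dates are moved to the first dose, and end-of-treatment biopsy events are largely captured.
- *About half of the biopsies precede the window, so about half of the harm is missed.* When the needle is used is not when an AE starts. With a Day 1 biopsy the pre-dose interval may be short; with a Screening biopsy it may be weeks. The share with pre-dose onset is unknown.
- *Participants biopsied but never dosed can simply be added to the denominator.* Footnote 13 to the schedule does foresee the case ("If a study biopsy was collected and the participant did not initiate study treatment"), but its purpose is to allow reuse of the tissue on rescreening. Protocol 5.4 treats such people as screen failures, for whom the minimal data set names SAEs but not non-serious AEs, and gives rescreened participants a new number. Protocol 8.3.2 is general, but complete non-serious data for this group cannot be assumed, and a combined rate could mix full and SAE-only capture.

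**Conclusion.** The concern holds for a defined class of events: complications of the adult baseline biopsy, in dosed participants, that start before the first dose, do not worsen afterwards and are not moved to the first-dose date by imputation. They are collected and attributed, then left out of the only table designed for them, and the SAP specifies no pre-treatment summary or AE listing in its place. The table can therefore understate procedure-related harm.

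The size cannot be stated from the documents. The range of 0.5 to 5.0 expected omissions rests on assumed values of q from 1% to 10% and on all 50 adults being biopsied. The primary endpoint and the drug-safety tables are unaffected. The change is worth making because, for dosed participants, the data are already collected and the present wording invites a conclusion about biopsy safety that the table cannot support.

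**What to change.** In SAP 6.12.1.1:

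1. Replace the procedure-related treatment-emergent summary with a summary of study procedure-related AEs and SAEs from informed consent, in the Safety Analysis Set, with onset before and after the first dose shown separately.
2. Add a biopsy row whose denominator is dosed participants who had a study biopsy.
3. State this as an exception to the rule that only treatment-emergent events are tabulated, and keep that rule for the drug-safety tables.
4. For participants biopsied but never dosed, list procedure-related SAEs and any recorded non-serious AEs separately. Note that the minimal screen-failure data set names only SAEs, and link rescreened participants across their participant numbers.

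While editing, correct the cross-reference for the treatment-emergent definition: 6.12.1.1 points to SAP 4.2.2.1 (Hematology), but the definition is in 4.2.1.1.

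For dosed participants the cost is SAP wording and one more table from data already collected. The never-dosed listing takes extra work to link records. The reported procedure-related AE rate may rise.
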